8.6.2 Safety/Tolerability

The safety analysis will be performed in the population valid for safety. All tabulations will be descriptive only. Tables will be produced for drug-related treatment-emergent adverse events and serious adverse events.

Mortality in the 6 month period of the study will be summarized descriptively. Any deaths in the study period will be listed, with day of death relative to start and stop of study drug and cause of death. Vital signs will be summarized by visit and treatment group.

8.6.2.1 Adverse events

Frequency tables of adverse events with classification of system organ class according to MedDRA classification will be provided. Adverse events will be provided according to suspected and no suspected relation to the study medication. Serious adverse events will be listed separately.

Hospitalisations due to worsening or adverse events will be listed.

8.6.2.2 Laboratory parameters

For the clinical parameters Laboratory: hemoglobin, hematocrit, AST, ALT, bilirubin, CRP, sodium, urea, creatinine, clearance, NT-proBNP arithmetic mean, median, standard deviation, standard error, median, first and third quartiles, minimum, and maximum for quantitative variables) for baseline and 6 month time points for each therapy group separately as well as frequency tables with number of values outside their limits of normal (or 3 x upper limit of normal for hepatic transaminases) will be displayed.

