### Exclusion Criteria

1. Any connective tissue diseases (CTD) other than SSc
2. Pulmonary hypertension (PH) confirmed by right heart catheter (RHC) before enrolment, i.e. mPAP  $\geq$ 25 mmHg at rest
3. Patients presenting normal mPAP values, i.e. mPAP <21 mmHg at rest, and  $\leq$ 30 mmHg during exercise, and/or PAWP  $\geq$ 15 mmHg at rest or  $\geq$ 18 mmHg during exercise
4. Ongoing or a history of >2 weeks of continued use of therapies that are considered definitive PH treatment: endothelin receptor antagonists (ERA; e.g. bosentan, ambrisentan), phosphodiesterase type 5 inhibitors (PDE5; e.g. sildenafil, tadalafil, vardenafil), prostanoids (e.g. epoprostenol, treprostinil, iloprost, beraprost) and soluble guanylate cyclase stimulator (e.g. Riociguat). Intermittent use of PDE5 inhibitors for male erectile dysfunction is permitted.
5. Except for diuretics and corticosteroids medical treatment should not be expected to change 4 weeks prior inclusion into the study and during the entire 12-week study period.
6. Known intolerance to ambrisentan or one of its excipients
7. Clinically significant anemia (hemoglobin concentration of less than 75% of the lower limit of normal, LLN)
8. Forced vital capacity (FVC) <60%, forced expiratory volume in first second (FEV1)

EudraCT: 2014-001882-28	3.1 Version 29.04.2016 final	EDITA
-------------------------	------------------------------	--------------

<65%

9. Severe interstitial lung disease, idiopathic pulmonary fibrosis
10. Renal insufficiency (glomerular filtration rate [GFR] <60 mL/min/1.73m^2 at least for the last 3 months before inclusion)
11. Baseline values of hepatic aminotransferases (ALT and/or AST) >3 x upper limit of normal (ULN)
12. Systolic blood pressure <85 mmHg;
13. evidence of inadequately treated blood pressure >160/90 mmHg and/or blood pressure during exercise >220/120 mmHg
14. Patients referred with clinically significant overt heart failure
15. Clinically significant fluid retention
16. Previous evidence or diagnosis of clinically relevant left heart disease, i.e. at least one of the following: Previous echocardiography with estimated left ventricular (LV) ejection fraction <50%, previous history of cardiogenic pulmonary edema, increased size of left atrium (>50 mm)
17. Known significant diastolic dysfunction associated with clinical heart failure
18. Known coronary disease or significant valvular heart disease

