# additional lab assessments for hepatic aminotransferases and haemoglobin will be performed at the patient’s general physician for safety reasons, reports will be faxed to the clinical site on a monthly basis

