13.1 Reference ranges of laboratory parameters

	male	female
Hemoglobin	♂ 0-3 Day(s) 14.5 - 22.5 g/dl	♀ 0-3 Day(s) 14.5 - 22.5 g/dl
	♂ 4-7 Day(s) 13.5 - 21.5 g/dl	♀ 4-7 Day(s) 13.5 - 21.5 g/dl
	♂ 8-14 Day(s) 14 - 20 g/dl	♀ 8-14 Day(s) 14 - 20 g/dl

	♂ 15-30 Day(s) 15 - 20 g/dl	♀ 15-30 Day(s) 15 - 20 g/dl
	♂ 31-182 Day(s) 9.5 - 13.5 g/dl	♀ 31-182 Day(s) 9.5 - 13.5 g/dl
	♂ 183-365 Day(s) 11 - 16 g/dl	♀ 183-365 Day(s) 11.0 - 16 g/dl
	♂ 1-6 Year(s) 11 - 14.5 g/dl	♀ 1-6 Year(s) 11 - 14.5 g/dl
	♂ 7-12 Year(s) 11.5 - 15 g/dl	♀ 7-12 Year(s) 11.5 - 15 g/dl
	♂ 13-18 Year(s) 12 - 16 g/dl	♀ 13-18 Year(s) 12 - 16 g/dl
	♂ 19-99 Year(s) 13 - 17 g/dl	♀ 19-99 Year(s) 12 - 15 g/dl
	male	female
Hematocrite	♂ 0-3 Day(s) 0.45 - 0.67 l/l	♀ 0-3 Day(s) 0.45 - 0.67 l/l
	♂ 4-7 Day(s) 0.42 - 0.66 l/l	♀ 4-7 Day(s) 0.42 - 0.66 l/l
	♂ 8-14 Day(s) 0.39 - 0.63 l/l	♀ 8-14 Day(s) 0.39 - 0.63 l/l
	♂ 15-30 Day(s) 0.45 - 0.64 l/l	♀ 15-30 Day(s) 0.45 - 0.64 l/l
	♂ 31-60 Day(s) 0.28 - 0.42 l/l	♀ 31-60 Day(s) 0.28 - 0.42 l/l
	♂ 61-365 Day(s) 0.35 - 0.44 l/l	♀ 61-365 Day(s) 0.35 - 0.44 l/l
	♂ 1-2 Year(s) 0.33 - 0.39 l/l	♀ 1-2 Year(s) 0.33 - 0.39 l/l
	♂ 3-6 Year(s) 0.31 - 0.37 l/l	♀ 3-6 Year(s) 0.31 - 0.37 l/l
	♂ 7-12 Year(s) 0.33 - 0.40 l/l	♀ 7-12 Year(s) 0.33 - 0.40 l/l
♂ 13-99 Year(s) 0.38 - 0.52 l/l	♀ 13-99 Year(s) 0.36 - 0.47 l/l	
	male	female
Thrombocytes	♂ 0-10 Day(s) 140 - 320 /nl	♀ 0-10 Day(s) 140 - 320 /nl
	♂ 11-30 Day(s) 150 - 380 /nl	♀ 11-30 Day(s) 150 - 380 /nl
	♂ 31-365 Day(s) 200 - 480 /nl	♀ 31-365 Day(s) 200 - 480 /nl
	♂ 1-10 Year(s) 180 - 530 /nl	♀ 1-10 Year(s) 180 - 530 /nl
	♂ 11-199 Year(s) 150 - 440 /nl	♀ 11-199 Year(s) 150 - 440 /nl
	male	female
Creatinine	♂ 0-1 Day(s) 0.4 - 1.3 mg/dl	♀ 0-1 Day(s) 0.4 - 1.3 mg/dl
	♂ 2-7 Day(s) 0.16 - 1.0 mg/dl	♀ 2-7 Day(s) 0.16 - 1.0 mg/dl
	♂ 8-30 Day(s) 0.1 - 0.6 mg/dl	♀ 8-30 Day(s) 0.1 - 0.6 mg/dl
	♂ 31-365 Day(s) 0.1 - 0.65 mg/dl	♀ 31-365 Day(s) 0.1 - 0.65 mg/dl
	♂ 1-6 Year(s) 0.3 - 0.8 mg/dl	♀ 1-6 Year(s) 0.3 - 0.8 mg/dl
	♂ 7-13 Year(s) 0.3 - 1.0 mg/dl	♀ 7-13 Year(s) 0.3 - 1.0 mg/dl
	♂ 14-17 Year(s) 0.3 - 1.2 mg/dl	♀ 14-17 Year(s) 0.3 - 1.2 mg/dl
	♂ 18-60 Year(s) 0.6 - 1.2 mg/dl	♀ 18-60 Year(s) 0.5 - 0.9 mg/dl
	♂ 61-70 Year(s) 0.6 - 1.3 mg/dl	♀ 61-70 Year(s) 0.5 - 1.0 mg/dl
	♂ 71-80 Year(s) 0.6 - 1.4 mg/dl	♀ 71-80 Year(s) 0.5 - 1.1 mg/dl
♂ 81-199 Year(s) 0.6 - 1.7 mg/dl	♀ 81-199 Year(s) 0.5 - 1.4 mg/dl	
	male	female
Potassium	♂ 0-30 Day(s) 3.6 - 6.0 mmol/l	♀ 0-30 Day(s) 3.6 - 6.0 mmol/l

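### The haemoglobin safety count in SAP 8.6.2.2 cannot show how many patients per arm fall below 75% of LLN, the level the protocol calls clinically significant anaemia

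*SAP*

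**What the plan says.** SAP 8.6.2.2 specifies two displays for haemoglobin. The first is a set of summary statistics that includes "first and third quartiles, minimum, and maximum for quantitative variables", given "for baseline and 6 month time points for each therapy group separately". The second is "frequency tables with number of values outside their limits of normal (or 3 x upper limit of normal for hepatic transaminases"). Aminotransferases are the only exception to the reference-range rule. The section specifies neither a shift table nor a severity category for haemoglobin.

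The protocol gives both of these laboratory risks a threshold at entry. Exclusion criterion 11 reads "Baseline values of hepatic aminotransferases (ALT and/or AST) >3 x upper limit of normal (ULN"). Exclusion criterion 7 reads "Clinically significant anemia (hemoglobin concentration of less than 75% of the lower limit of normal, LLN"). The protocol also singles out the same two for monitoring beyond the site visits. The footnote to the trial schedule (section 1.1) says that "additional lab assessments for hepatic aminotransferases and haemoglobin will be performed" by the general physician, with monthly reports to the site.

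The adult haemoglobin ranges in SAP 13.1 are "19-99 Year(s) 13 - 17 g/dl" for men and "19-99 Year(s) 12 - 15 g/dl" for women.

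**The concern.** The SAP treats the two specially monitored risks differently. For aminotransferases the count uses the same multiple as the entry criterion. An eligible patient therefore starts outside the count, and any later entry is a new crossing. For haemoglobin the count uses LLN, while the entry criterion sits well below it. Everyone admitted between 75% and 100% of LLN is counted at baseline and remains counted at 6 months, however far the value falls.

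The count can also order falls the wrong way. A woman going from 12.1 to 11.9 g/dl adds one to it, while a woman going from 11.5 to 8.8 g/dl adds nothing.

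Timing adds a second gap. Only baseline and 6 months are tabulated, and SAP 7.1 uses complete cases without imputation. A patient whose haemoglobin falls and who then leaves early has no 6-month value to count.

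At stake is the usefulness of the safety report on a risk the protocol chose to watch. With 19 patients planned per arm and descriptive safety tables only (SAP 8.6.2), counts of individual threshold crossings are among the most informative summaries available.

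**Working it through.** The documents give no figure to reproduce here. The check is to classify values under each rule.

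**Inputs.** LLN is 13 g/dl for men and 12 g/dl for women aged 19-99 (SAP 13.1). The anaemia threshold is below 75% of LLN (exclusion criterion 7). The plan is 19 patients per arm (protocol, Sample Size). The patient values below are illustrations, not data from the documents.

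**Step 1: threshold in g/dl.**
- Men: 0.75 × 13 = 9.75
- Women: 0.75 × 12 = 9.0
- At age 18, SAP 13.1 gives 12-16 g/dl for both sexes, so the threshold is again 0.75 × 12 = 9.0.

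**Step 2: values admitted by criterion 7 but already below the reference range.**
- Men: 9.75 to below 13, a band of 13 − 9.75 = 3.25 g/dl
- Women: 9.0 to below 12, a band of 12 − 9.0 = 3.0 g/dl

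**Step 3: classify example patients under both rules.**

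| Patient | Baseline → 6 months (g/dl) | Outside reference range | Below 75% of LLN |
|---|---|---|---|
| Woman | 11.5 → 8.8 | 1 → 1 | 0 → 1 |
| Man | 12.5 → 9.74 | 1 → 1 | 0 → 1 |
| Woman | 12.1 → 11.9 | 0 → 1 | 0 → 0 |

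The first woman's fall is 11.5 − 8.8 = 2.7 g/dl, and 2.7 / 11.5 = 23%.

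**Step 4: effect on the arm summaries.**
- Mean: 2.7 / 19 = 0.14 g/dl with all 19 measured, or 2.7 / 15 = 0.18 g/dl with 15 measured (the sample size before the drop-out allowance).
- Reference-range count: unchanged.
- A row for below 75% of LLN: 0/19 to 1/19 = 5.3% for one such patient, and to 2/19 = 10.5% for two.

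**Step 5: what the other planned outputs show.**
- *Arm minimum (SAP 8.6.2.2).* It gives one value per arm, not a number of patients. With the sexes pooled, a minimum from 9.0 to 9.74 g/dl is below the threshold for a man but not for a woman.
- *Change from baseline (SAP 8.2).* If applied to haemoglobin, its minimum gives the largest fall, but not the starting level or whether the threshold was crossed.
- *Listings (protocol, Statistical Analysis).* They let a reader trace each patient but give no count by arm.
- *Adverse event tables (SAP 8.6.2.1).* They show the fall only if it was reported as an event.

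**The case against.** The strongest reply is that the fall is not hidden. The sentence that sets the counting rule also requires the minimum for each arm. A value of 8.8 g/dl would appear there unless another patient were lower, and it is below 75% of LLN for either sex. Change-from-baseline summaries, listings for only 38 patients and adverse event tables give further routes. All of this stands. A reader might infer that clinically significant anaemia would go undetected or that the safety conclusion would be wrong. The documents support neither. Safety tabulations are descriptive, no test or decision rule depends on this count, and a coarse count is not a false one.

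The second reply is that 75% of LLN is an entry criterion. A reader might infer that the SAP contradicts the protocol by not using it. It does not, because nothing in the available text makes 75% of LLN an on-treatment limit or a reporting category. Matching 3 × ULN to criterion 11 does not oblige the SAP to reuse every exclusion cut-off. The SAP also mentions withdrawal criteria (sections 2 and 9) that the available protocol text does not set out, so whether on-treatment haemoglobin limits exist elsewhere is unknown. This reply also stands, and it makes the gap a missing severity category, not an inconsistency.

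Third, a reader might infer that low and high values will be pooled. The wording permits that but does not require it. If they were pooled, a woman going from 15.2 to 11.8 g/dl (a fall of 3.4) would count as abnormal at both visits. This needs clarifying but is not an established defect.

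What the replies leave untouched is that no planned output gives the number of patients per arm who crossed the protocol's own anaemia threshold.

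**Conclusion.** The point holds as an inexpensive improvement to the reporting. The planned haemoglobin count does not respond to a fall from the 75-100% band to below 75% of LLN, and its 6-month column omits patients who left earlier. Within its scope it is insensitive and incomplete.

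The size per patient is clear: one crossing changes the planned count by 0 and a threshold row by 1 in 19. The size for the trial is unknown, because the documents do not say how many patients will enter below LLN or how many of those will fall further. If nobody enters below LLN, the baseline masking of low values does not arise, although the count still would not separate mild from marked falls.

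The conclusion assumes that the SAP 13.1 ranges are the ones applied, and that each baseline value used in the table still satisfies criterion 7.

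**What to change.** In SAP 8.6.2.2:

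1. Add, per arm, a haemoglobin shift table from baseline to the lowest post-baseline site-visit value (Visits 3 and 4). Use three categories: at or above LLN, from 75% to below 100% of LLN, and below 75% of LLN (below 9.75 g/dl for men, below 9.0 g/dl for women). Using the lowest value keeps in the table any patient who has a Visit 3 result but leaves before Visit 4.
2. Count low and high values separately.
3. State whether the monthly values faxed by general physicians are included.

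The 75% cut-off is meant here as a reporting category only and implies no rule for managing patients.

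The cost is SAP wording and one extra descriptive table. Site-visit values need no new collection, since the trial schedule already has local laboratory assessments at Visits 3 and 4. Including the monthly values may need some data entry, because the documents do not show that the faxed reports reach the analysis database.

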8.6.2.3 Vital signs

For diastolic and systolic blood pressure, heart rate and weight we will list arithmetic mean, median, standard deviation, standard error, first and third quartiles, minimum, and maximum for quantitative variables for baseline and 6 month time point for each therapy group.

Furthermore, frequency tables of pathologic findings in the physical examination will be displayed.

8.6.3 Quality of life

Quality of life scales (QoL, SF-36) are secondary efficacy parameters. Their change from baseline to 6 months will be compared with the same methods as for the primary parameter.

9 Deviations from the protocol

Description and explanation of deviations regarding withdrawal criteria, in- and exclusion criteria, adherence to time window and treatment compliance will be provided.

Major protocol deviations are:

1. Patients who do not meet the inclusion criteria

2. Administration of study medication not according to protocol (e.g. compliance less than 80% or greater 120%); Discrepancies of study medication intake are noted as comments in the CRF.

10 Interpretation of results

Effect size estimation and description

Clinical worsening on the individual level is defined as 15% higher mPAP values at 6 months compared to baseline. Clinically significant improvement is defined as 15% lower mPAP values at 6 months compared to baseline.

Scatterplots of baseline versus 6-month measurements will be plotted with a linear fit for therapy. In case of outliers or extreme values robust fits will be used. Frequency tables with patients who have a clinically relevant worsening/improvement after 6 months of therapy will be displayed.

Descriptive analysis of differences of secondary parameters.

Secondary efficacy parameters will be screened whether they support the results of the primary endpoint or not.

11 Software

SPSS V24, SAS JMP 14

12 References

https://www.jmp.com/en_us/support/online-help.html

(last queried 17.7.2018)

<https://www-01.ibm.com/support/docview.wss?uid=swg27047033>

(last queried 17.7.2018)

13 Appendices

13.1 Reference ranges of laboratory parameters

	male	female
Hemoglobin	♂ 0-3 Day(s) 14.5 - 22.5 g/dl	♀ 0-3 Day(s) 14.5 - 22.5 g/dl
	♂ 4-7 Day(s) 13.5 - 21.5 g/dl	♀ 4-7 Day(s) 13.5 - 21.5 g/dl
	♂ 8-14 Day(s) 14 - 20 g/dl	♀ 8-14 Day(s) 14 - 20 g/dl

	♂ 15-30 Day(s) 15 - 20 g/dl	♀ 15-30 Day(s) 15 - 20 g/dl
	♂ 31-182 Day(s) 9.5 - 13.5 g/dl	♀ 31-182 Day(s) 9.5 - 13.5 g/dl
	♂ 183-365 Day(s) 11 - 16 g/dl	♀ 183-365 Day(s) 11.0 - 16 g/dl
	♂ 1-6 Year(s) 11 - 14.5 g/dl	♀ 1-6 Year(s) 11 - 14.5 g/dl
	♂ 7-12 Year(s) 11.5 - 15 g/dl	♀ 7-12 Year(s) 11.5 - 15 g/dl
	♂ 13-18 Year(s) 12 - 16 g/dl	♀ 13-18 Year(s) 12 - 16 g/dl
	♂ 19-99 Year(s) 13 - 17 g/dl	♀ 19-99 Year(s) 12 - 15 g/dl
	male	female
Hematocrite	♂ 0-3 Day(s) 0.45 - 0.67 l/l	♀ 0-3 Day(s) 0.45 - 0.67 l/l
	♂ 4-7 Day(s) 0.42 - 0.66 l/l	♀ 4-7 Day(s) 0.42 - 0.66 l/l
	♂ 8-14 Day(s) 0.39 - 0.63 l/l	♀ 8-14 Day(s) 0.39 - 0.63 l/l
	♂ 15-30 Day(s) 0.45 - 0.64 l/l	♀ 15-30 Day(s) 0.45 - 0.64 l/l
	♂ 31-60 Day(s) 0.28 - 0.42 l/l	♀ 31-60 Day(s) 0.28 - 0.42 l/l
	♂ 61-365 Day(s) 0.35 - 0.44 l/l	♀ 61-365 Day(s) 0.35 - 0.44 l/l
	♂ 1-2 Year(s) 0.33 - 0.39 l/l	♀ 1-2 Year(s) 0.33 - 0.39 l/l
	♂ 3-6 Year(s) 0.31 - 0.37 l/l	♀ 3-6 Year(s) 0.31 - 0.37 l/l
	♂ 7-12 Year(s) 0.33 - 0.40 l/l	♀ 7-12 Year(s) 0.33 - 0.40 l/l
♂ 13-99 Year(s) 0.38 - 0.52 l/l	♀ 13-99 Year(s) 0.36 - 0.47 l/l	
	male	female
Thrombocytes	♂ 0-10 Day(s) 140 - 320 /nl	♀ 0-10 Day(s) 140 - 320 /nl
	♂ 11-30 Day(s) 150 - 380 /nl	♀ 11-30 Day(s) 150 - 380 /nl
	♂ 31-365 Day(s) 200 - 480 /nl	♀ 31-365 Day(s) 200 - 480 /nl
	♂ 1-10 Year(s) 180 - 530 /nl	♀ 1-10 Year(s) 180 - 530 /nl
	♂ 11-199 Year(s) 150 - 440 /nl	♀ 11-199 Year(s) 150 - 440 /nl
	male	female
Creatinine	♂ 0-1 Day(s) 0.4 - 1.3 mg/dl	♀ 0-1 Day(s) 0.4 - 1.3 mg/dl
	♂ 2-7 Day(s) 0.16 - 1.0 mg/dl	♀ 2-7 Day(s) 0.16 - 1.0 mg/dl
	♂ 8-30 Day(s) 0.1 - 0.6 mg/dl	♀ 8-30 Day(s) 0.1 - 0.6 mg/dl
	♂ 31-365 Day(s) 0.1 - 0.65 mg/dl	♀ 31-365 Day(s) 0.1 - 0.65 mg/dl
	♂ 1-6 Year(s) 0.3 - 0.8 mg/dl	♀ 1-6 Year(s) 0.3 - 0.8 mg/dl
	♂ 7-13 Year(s) 0.3 - 1.0 mg/dl	♀ 7-13 Year(s) 0.3 - 1.0 mg/dl
	♂ 14-17 Year(s) 0.3 - 1.2 mg/dl	♀ 14-17 Year(s) 0.3 - 1.2 mg/dl
	♂ 18-60 Year(s) 0.6 - 1.2 mg/dl	♀ 18-60 Year(s) 0.5 - 0.9 mg/dl
	♂ 61-70 Year(s) 0.6 - 1.3 mg/dl	♀ 61-70 Year(s) 0.5 - 1.0 mg/dl
	♂ 71-80 Year(s) 0.6 - 1.4 mg/dl	♀ 71-80 Year(s) 0.5 - 1.1 mg/dl
♂ 81-199 Year(s) 0.6 - 1.7 mg/dl	♀ 81-199 Year(s) 0.5 - 1.4 mg/dl	
	male	female
Potassium	♂ 0-30 Day(s) 3.6 - 6.0 mmol/l	♀ 0-30 Day(s) 3.6 - 6.0 mmol/l
	♂ 31-365 Day(s) 3.5 - 5.7 mmol/l	♀ 31-365 Day(s) 3.5 - 5.7 mmol/l
	♂ 1-17 Year(s) 3.5 - 4.8 mmol/l	♀ 1-17 Year(s) 3.5 - 4.8 mmol/l
	♂ 18-40 Year(s) 3.4 - 4.6 mmol/l	♀ 18-40 Year(s) 3.4 - 4.6 mmol/l
	♂ 41-60 Year(s) 3.4 - 4.8 mmol/l	♀ 41-60 Year(s) 3.4 - 4.8 mmol/l
	♂ 61-199 Year(s) 3.4 - 5.0 mmol/l	♀ 61-199 Year(s) 3.4 - 5.0 mmol/l
	male	female
SGOT/ASAT	♂ 0-180 Day(s) <74 U/l	♀ 0-180 Day(s) <74 U/l

Serum-Glutamate-Oxalacetate-Transaminase	♂ 181-365 Day(s) <52 U/l	♀ 181-365 Day(s) <52 U/l
	♂ 1-5 Year(s) <43 U/l	♀ 1-5 Year(s) <43 U/l
	♂ 6-14 Year(s) <39 U/l	♀ 6-14 Year(s) <39 U/l
	♂ 15-17 Year(s) <50 U/l	♀ 15-17 Year(s) <35 U/l
	♂ 18-199 Year(s) <46 U/l	♀ 18-199 Year(s) <37 U/l
	male	female
SGPT/ALT Serum-Glutamate-Pyruvate-Transaminase	♂ 0-180 Day(s) <60 U/l	♀ 0-180 Day(s) <60 U/l
	♂ 181-365 Day(s) <43 U/l	♀ 181-365 Day(s) <43 U/l
	♂ 1-199 Year(s) <50 U/l	♀ 1-199 Year(s) <35 U/l
	male	female
LDH Lactate dehydrogenase	♂ 0-30 Day(s) <780 U/l	♀ 0-30 Day(s) <780 U/l
	♂ 31-365 Day(s) <416 U/l	♀ 31-365 Day(s) <416 U/l
	♂ 1-5 Year(s) <364 U/l	♀ 1-5 Year(s) <364 U/l
	♂ 6-14 Year(s) <312 U/l	♀ 6-14 Year(s) <312 U/l
	♂ 15-17 Year(s) <248 U/l	♀ 15-17 Year(s) <248 U/l
	♂ 18-40 Year(s) <316 U/l	♀ 18-40 Year(s) <264 U/l
	♂ 41-60 Year(s) <317 U/l	♀ 41-60 Year(s) <308 U/l
♂ 61-199 Year(s) <342 U/l	♀ 61-199 Year(s) <301 U/l	
	male	female
CK Creatinkinase	♂ 0-3 Day(s) <777 U/l	♀ 0-3 Day(s) <777 U/l
	♂ 4-10 Day(s) <420 U/l	♀ 4-10 Day(s) <420 U/l
	♂ 11-365 Day(s) <286 U/l	♀ 11-365 Day(s) <286 U/l
	♂ 1-199 Year(s) <190 U/l	♀ 1-199 Year(s) <170 U/l
	male	female
CRP	♂ 0- Year(s) <5 mg/l	♀ 0- Year(s) <5 mg/l
	male	female
NTproBNP	♂ 0-70 Year(s) <125 ng/l	♀ 0-70 Year(s) <125 ng/l
	♂ 71- Year(s) <450 ng/l	♀ 71- Year(s) <450 ng/l
β-HCG		negative
